12. DATA REPORTING / REGULATORY REQUIREMENTS

Adverse event lists, guidelines, and instructions for AE reporting can be found in section 7 (Adverse Events: List and Reporting Requirements).

12.1 Data Reporting

12.1.1 Responsibility for Data Submission

Pre-treatment, on-study and off-treatment data, as well as patient response data are to be recorded in the electronic data collection screens using the PBTC RDC database. See the Required Data and Timetable for Submission form located on the 033 Protocol webpage for the schedule. For assistance, contact the PBTC Protocol Coordinator, [name] at [contact], email: [contact]. An optional roadmap is located on the PBTC-033 Protocol Webpage.

12.1.2 Method

This study will be monitored by the Clinical Data Update System (CDUS) Version 3.0. Cumulative protocol- and patient-specific CDUS data will be submitted electronically to CTEP on a quarterly basis, either by FTP burst of data or via the CDS web application. Reports are due January 31, April 30, July 31, and October 31. Instructions for submitting data using the CDUS can be found on the CTEP Web site (http://ctep.cancer.gov/reporting/cdus.html).

12.2 CTEP Multicenter Guidelines

12.3 Collaborative Agreements Language

The agent(s) supplied by CTEP, DCTD, NCI used in this protocol is/are provided to the NCI under a Collaborative Agreement (CRADA, CTA, CSA) between the Pharmaceutical Company(ies) (hereinafter referred to as "Collaborator(s)") and the NCI Division of Cancer Treatment and Diagnosis. Therefore, the following obligations/guidelines, in addition to the provisions in the "Intellectual Property Option to Collaborator"

(http://ctep.cancer.gov/industryCollaborations2/intellectual_property.htm) contained within the terms of award, apply to the use of the Agent(s) in this study:

- Agent(s) may not be used for any purpose outside the scope of this protocol, nor can Agent(s) be transferred or licensed to any party not participating in the clinical study. Collaborator(s) data for Agent(s) are confidential and proprietary to Collaborator(s) and shall be maintained as such by the investigators. The protocol documents for studies utilizing Agents contain confidential information and should not be shared or distributed without the permission of the NCI. If a copy of this protocol is requested by a patient or patient's family member participating on the study, the individual should sign a confidentiality agreement. A suitable model agreement can be downloaded from: http://ctep.cancer.gov.
- 2. For a clinical protocol where there is an investigational Agent used in combination with (an)other Agent(s), each the subject of different Collaborative Agreements, the access to and use of data by each Collaborator shall be as follows (data pertaining to such combination use shall hereinafter be referred to as "Multi-Party Data"):
 - a. NCI will provide all Collaborators with prior written notice regarding the existence and nature of any agreements governing their collaboration with NCI, the design of the proposed combination protocol, and the existence of any obligations that would tend to

N/A

restrict NCI's participation in the proposed combination protocol.

- b. Each Collaborator shall agree to permit use of the Multi-Party Data from the clinical trial by any other Collaborator solely to the extent necessary to allow said other Collaborator to develop, obtain regulatory approval or commercialize its own Agent.
- c. Any Collaborator having the right to use the Multi-Party Data from these trials must agree in writing prior to the commencement of the trials that it will use the Multi-Party Data solely for development, regulatory approval, and commercialization of its own Agent.
- 3. Clinical Trial Data and Results and Raw Data developed under a Collaborative Agreement will be made available to Collaborator(s), the NCI, and the FDA, as appropriate and unless additional disclosure is required by law or court order as described in the IP Option to Collaborator (http://ctep.cancer.gov/industryCollaborations2/intellectual_property.htm). Additionally, all Clinical Data and Results and Raw Data will be collected, used and disclosed consistent with all applicable federal statutes and regulations for the protection of human subjects, including, if applicable, the *Standards for Privacy of Individually Identifiable Health Information* set forth in 45 C.F.R. Part 164.
- 4. When a Collaborator wishes to initiate a data request, the request should first be sent to the NCI, who will then notify the appropriate investigators (Group Chair for Cooperative Group studies, or PI for other studies) of Collaborator's wish to contact them.
- 5. Any data provided to Collaborator(s) for Phase 3 studies must be in accordance with the guidelines and policies of the responsible Data Monitoring Committee (DMC), if there is a DMC for this clinical trial.
- 6. Any manuscripts reporting the results of this clinical trial must be provided to CTEP by the Group office for Cooperative Group studies or by the principal investigator for non-Cooperative Group studies for immediate delivery to Collaborator(s) for advisory review and comment prior to submission for publication. Collaborator(s) will have 30 days from the date of receipt for review. Collaborator shall have the right to request that publication be delayed for up to an additional 30 days in order to ensure that Collaborator's confidential and proprietary data, in addition to Collaborator(s)'s intellectual property rights, are protected. Copies of abstracts must be provided to CTEP for forwarding to Collaborator(s) for courtesy review as soon as possible and preferably at least three (3) days prior to submission, but in any case, prior to presentation at the meeting or publication in the proceedings. Press releases and other media presentations must also be forwarded to CTEP prior to release. Copies of any manuscript, abstract and/or press release/ media presentation should be sent to:

Email: [contact]

The Regulatory Affairs Branch will then distribute them to Collaborator(s). No publication, manuscript or other form of public disclosure shall contain any of Collaborator's confidential/ proprietary information.

13. STATISTICAL CONSIDERATIONS

13.1 Phase I Study Design/Endpoints

13.1.1 Dose Finding

This phase of the trial is being implemented in order to determine maximum tolerated dose or recommended Phase II of ABT-888 that can safely be delivered with RT in the context of carrying it forward to the efficacy (Phase II) component of this study. The traditional 3+3 dose finding algorithm will be used. Initially 3 patients will be enrolled on dose level 1 and will be observed for dose limiting toxicities during the first 10 weeks (6-7 weeks of radiation therapy followed by a rest period), which is the DLT observation period. If none of these three patients experience a DLT, escalation to dose level 2 will occur. If, on the other hand, 1 out of three patients experience a DLT, then 3 additional patients will be treated at dose level 1. If at most 1 DLT is observed in these 6 patients, escalation to dose level 2 will occur. Otherwise, if 2 or more DLTs are observed in dose level 1, then de-escalation to dose level 0 will take place and the same process will be repeated. The highest dose level with fewer than 2 DLTs in 6 patients will be carried forward to the Phase II component of this study. If dose level 0 is determined to be too toxic (i.e. more than 1 DLT), then the trial will be closed to accrual and the approach will be re-evaluated.

13.1.2 Definition of Evaluable Patient

Patients who receive at least 1 dose of the study regimen and are removed from treatment for toxicity during the dose-finding period are evaluable for estimating the MTD/recommended Phase II dose as long as no additional anti-cancer therapy or supportive care that would confound the interpretation of any observed toxicity or side effect is given.

Patients who receive at least 85% of prescribed therapy during the dose-finding period but who progress prior to completing the rest/evaluation period may be considered evaluable for estimating the MTD, as long as no additional anti-cancer therapy or supportive care that would confound the interpretation of any observed toxicity or side effect is given. Patients should have completed all of the clinical and laboratory monitoring requirements specified by the protocol up to the time of disease progression for them to be considered evaluable for MTD/recommended Phase II dose.

Patients who receive less than 85% of the protocol specified therapy and who go off treatment for reasons other than toxicity (e.g. progressive disease, withdrawal of consent etc.) will be considered inevaluable for estimating the MTD/recommended Phase II and will be replaced.

Patients who complete all therapy during the dose-finding period but who fail to comply with all the specified clinical and laboratory monitoring requirements for the dose finding period may be considered inevaluable by the study chair for estimating the MTD/recommended Phase II and may be replaced.

13.1.3 Feasibility Assessment of Intra-patient Dose Escalation (for patients treated in both Phase I and Phase II of the study):

During maintenance therapy, in an effort to maximize the TMZ dose for each patient, intrapatient dose escalation will be studied. All patients will initiate maintenance treatment with

25 mg/m² ABT-888 and 135 mg/m² of TMZ with a possibility to escalate to 175 mg/m² and to 200 mg/m² of TMZ, if no unacceptable toxicities occur following 1 course of treatment at each of these dose levels (**Table 12**). More specifically, intra-patient dose escalation will only be considered if a patient meets the escalation criterion following the first course of TMZ as part of maintenance therapy. Intra-patient dose escalation will be assessed only in patients who are eligible to escalate and escalation to a given dose will be halted based on similar rules employed in traditional 3+3 designs, i.e. if 2 out of first 2-6 patients, 4 out of first 12 patients, etc. experience dose modifying toxicities during their first course of therapy at a given dose level. . This stopping rule will be applied for patients enrolled during the Phase I and Phase II components of the study. Even though these stopping rules will only be enforced during the first course of treatment at a given dose level for TMZ, we will periodically monitor for the occurrence of dose modifying toxicities in later courses and may revise this approach in the event that excessive toxicities are observed.

13.2 Phase II Study Design/Endpoints:

The primary efficacy endpoint of this phase II trial is overall survival defined as the time from initiation of therapy to the date of death from any cause or to the date patient was known to be alive for surviving patients. Progression-free survival (PFS) is a secondary endpoint and is defined as the time from initiation of treatment to the earliest date of failure (disease progression, death from any cause, or second malignancy) for patients who fail and to the last assessment date for patients who have not failed. Patients who start other anti-cancer therapy prior to disease progression will be censored in the Kaplan-Meier estimate of PFS as of the date the alternative therapy began. Patients who have not failed (died) at the time of analyses will be censored at their last date of contact in the Kaplan-Meier estimate of the PFS (overall survival) distribution.

The primary objective of this part of the study will be assessed based on the intent-to-treat (ITT) hypothesis. That is, any eligible patient who receives any ABT-888 will be included in the primary analysis. Note that patients who were treated at the recommended Phase II dose of ABT-888 concurrently with RT during the Phase I component of the study and who meet the eligibility criteria for Phase II will be counted towards the accrual goal of the latter.

[figure not shown]

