6.1 Dose Modification for DLT during ABT-888 and Radiation

6.1.1 Non-Hematologic

For ABT-888-related non-hematologic DLTs during radiation therapy, ABT-888 will be withheld until the toxicity resolves to meet on study parameters (section 3.1.6), and the patient will restart ABT-888 at one dose level lower (see **Table 10**), if not already at Dose Level 0. Patients who experience a non-hematologic DLT on Dose Level 0 will complete radiation without ABT-888.

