6.1.2 Hematologic

For ABT-888-related hematologic DLTs, ABT-888 will be withheld until criteria described below are met, and ABT-888 will be restarted at one dose level lower, if not already at Dose Level 0. If the same DLT is experienced at the lower dose level, then ABT-888 should be discontinued. If a different DLT is encountered, then the patient may restart ABT-888 at the next lower dose level, if not already at Dose Level 0.

In the event of hematological DLT, CBC should be checked twice weekly until recovery of ANC $\geq 1,000/\text{mm}^3$ and platelet $\geq 100,000/\text{mm}^3$. A patient who experiences any DLT despite being treated at Dose Level 0 will complete radiation therapy without ABT-888. Irradiation should be continued despite ABT-888-related DLT, unless there is a clinical contraindication.

- a. \geq Grade 3 thrombocytopenia: Platelet transfusion is permissible and strongly encouraged for patients with dose-limiting thrombocytopenia to minimize the risk of intra-tumoral hemorrhage. ABT-888 should not be restarted until platelet count has recovered to \geq 100,000/mm³ (transfusion independent). Radiation therapy should not be interrupted unless clinically indicated.
- b. Patients with grade 4 neutropenia may receive filgrastim (G-CSF) support only for documented infection and/or sepsis, and they should re-start ABT-888 at the next lower dose level without GCSF support. ABT-888 should not be restarted until the ANC is ≥1,000/mm³ for at least 48 hours without G-CSF support. Radiation therapy should not be interrupted unless clinically indicated.

Patients who experience ABT-888-related DLTs during irradiation will still receive ABT-888 during maintenance therapy, provided that they meet the criteria to start subsequent course of

therapy and all prior ABT-888-related toxicities have resolved to baseline.

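### Section 13.1.2 does not make every patient with a DLT evaluable, so an observed DLT can be replaced out of the 3+3 count; the recommended Phase II dose could then be too high if DLT patients are dropped more often than others

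*Combined protocol and SAP*

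**What the plan says.** Section 13.1.2 (Definition of Evaluable Patient) sets out who counts in Phase I.

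- **Protected.** Patients with at least one dose who "are removed from treatment for toxicity during the dose-finding period are evaluable", but only "as long as no additional anti-cancer therapy or supportive care that would confound the interpretation of any observed toxicity or side effect is given".
- **Possibly evaluable.** Patients with at least 85% of prescribed therapy who progress before the rest period ends. The same supportive-care condition applies, and monitoring must be complete up to progression.
- **Mandatory replacement.** "Patients who receive less than 85% of the protocol specified therapy and who go off treatment for reasons other than toxicity": these "will be considered inevaluable for estimating the MTD/recommended Phase II and will be replaced".
- **Discretionary replacement.** Patients who complete therapy but miss required monitoring "may be considered inevaluable by the study chair for estimating the MTD/recommended Phase II and may be replaced".

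None of these rules refers to whether the patient had a DLT. Sections 5.1.1.1, 5.2 and 13.1.1 do not supply a rule that every DLT counts regardless of evaluability.

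Section 6.1 describes what follows a DLT during radiation. After a non-hematologic DLT the drug is held and "the patient will restart ABT-888 at one dose level lower". After a hematologic DLT, "ABT-888 will be restarted at one dose level lower, if not already at Dose Level 0". At Dose Level 0 radiation is completed without ABT-888. Section 6.1.2 adds: "Platelet transfusion is permissible and strongly encouraged for patients with dose-limiting thrombocytopenia".

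**The concern.** The protecting rule turns on removal from treatment for toxicity, but under section 6.1 the usual sequel to a DLT is a hold and a restart. Section 5.2.1.4 even defines an ABT-888-related event that leads to a dose reduction as a DLT, so the protocol expects DLTs in patients who stay on treatment. Such a patient is outside the protecting rule and open to rules written without DLTs in mind.

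A 3+3 design decides on very small counts. Replacing one DLT patient with a DLT-free one changes 1/3 (expand) into 0/3 (escalate), or 2/6 (too toxic) into 1/6 (acceptable). The chosen level goes into a Phase II of 60 patients. Phase I patients treated at that level and eligible for Phase II count toward the 60, so if six do, 60 − 6 = 54 further children would start at it.

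**Working it through.** **1. The plan's own Phase I figure.** Section 13.3 expects 12-18 patients on 2-3 levels: 2 × 6 = 12 and 3 × 6 = 18. It reproduces exactly, with no allowance for replaced patients. The plan gives no operating characteristics for the 3+3 rule.

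**2. Ways an observed DLT can leave the count (13.1.2 read against 6.1).**

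- (a) DLT, hold or reduction, under 85% of therapy, then off treatment for progression or withdrawal: replacement is mandatory.
- (b) DLT, therapy completed, a monitoring requirement missed: the study chair may exclude and replace.
- (c) DLT, supportive care judged confounding: the protecting rule no longer applies. Section 6.1.2 encourages platelet transfusion for one type of DLT, and 13.1.2 does not say whether that is confounding.

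**3. How easily a DLT patient falls below 85%.** Section 5.1.1 gives 30 fractions with twice-daily ABT-888, so about 60 doses; 0.85 × 60 = 51. Missing 10 doses, a hold of five treatment days, leaves 50/60 = 83%. If 85% is counted in mg of the assigned dose, a reduction from 50 to 35 mg/m² (ratio 0.70) with a fraction f of doses at the full level gives f + 0.70(1 − f), which is below 0.85 whenever f < 0.50. A reduction before mid-radiation is then enough without a hold. The section does not define which measure applies.

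**4. Effect on the counted DLT rate.** Let p be the true DLT rate, r the share of DLT patients replaced and s the share of DLT-free patients replaced. The DLT rate among counted patients is

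p′ = p(1 − r) / [p(1 − r) + (1 − p)(1 − s)].

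If r = s, then p′ = p and there is no bias. If r > s, then p′ < p. The documents give no value for p, r or s; those below are assumptions.

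**5. Effect on the 3+3 rule.** From section 13.1.1, with q = 1 − p:

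- escalate past a level (0/3, or 1/3 then 0/3): q³ + 3pq⁵
- meet the selection rule (at most 1 DLT in 6): q⁶ + 6pq⁵

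At p = 0.40 with r = 0: escalation 0.216 + 0.093 = 0.309; selection 0.047 + 0.187 = 0.233.

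At p = 0.40, r = 0.20, s = 0: p′ = 0.32/0.92 = 0.348; escalation 0.277 + 0.123 = 0.401; selection 0.077 + 0.246 = 0.323.

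Range, with s = 0 throughout:

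| True DLT rate | DLT patients replaced | p′ | Escalate past level | At most 1 in 6 |
|---|---|---|---|---|
| 40% | 0% | 0.400 | 31% | 23% |
| 40% | 5% | 0.388 | 33% | 25% |
| 40% | 10% | 0.375 | 35% | 27% |
| 40% | 20% | 0.348 | 40% | 32% |
| 40% | 30% | 0.318 | 46% | 38% |
| 30% | 0% | 0.300 | 49% | 42% |
| 30% | 5% | 0.289 | 52% | 44% |
| 30% | 10% | 0.278 | 54% | 47% |
| 30% | 20% | 0.255 | 59% | 52% |
| 30% | 30% | 0.231 | 64% | 58% |

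Replacing some DLT-free patients as well shrinks the effect. At p = 0.40, r = s = 0.20 returns escalation to 31%.

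**The case against.** The strongest case on the other side has four parts.

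**Off-treatment list.** Section 5.5.1 names unacceptable toxicity, with reference to 5.2, as a reason to go off treatment. Since 5.2 defines DLTs, a DLT patient might be held to be off treatment for toxicity and so protected. This does not sit with 6.1, which keeps such patients on treatment, and it leaves routes (b) and (c) open. The two sections need reconciling and cannot serve as the safeguard as they stand.

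**Rarity.** Route (a) needs a DLT, less than 85% of therapy and a non-toxicity exit in one patient within 10 weeks, in a Phase I of 12-18 patients. This stands: the share replaced may well be small, which is why the 5% and 10% rows matter.

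**The 85% threshold.** Radiation is part of protocol therapy and usually continues after a DLT, and holds under 6.1 are themselves specified by the protocol. On such a reading a DLT patient need not fall below 85%. This also stands, because the measure is undefined.

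**Discretion.** Route (b) is optional, and nothing suggests that the study chair would discard a documented DLT. True, but the text does not prevent it.

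A reader might go further and infer that the rules drop DLT patients only, so that an upward bias is certain. The text does not support that: both replacement rules also apply to DLT-free patients, and equal removal rates give no bias. A reader might also take the escalation figures as the chance that a level is chosen for Phase II. They are not. Section 13.1.1 selects the highest level with fewer than 2 DLTs in 6, for which the at-most-1-in-6 column is the relevant one, and even that describes a single level, not the whole dose path.

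**Conclusion.** The gap is real: followed as written, 13.1.2 can replace a patient whose DLT was observed, by one mandatory and two judgement-dependent routes. Patients taken off treatment for toxicity without confounding care are protected.

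The recommended Phase II dose would be biased upward only if DLT patients are dropped more often than DLT-free patients. Holds and reductions after a DLT make that plausible, because they push those patients toward the 85% threshold, but the documents do not measure it. At a true DLT rate of 40% and no DLT-free replacements, the gain in the chance of escalating is about 2 points at a 5% replacement share and about 15 points at 30%; the selection probability moves by similar amounts. These figures are illustrative and rest on assumed values of p, r and s. The point warrants a change because the safeguard is cheap and the counts that drive the dose decision are small.

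**What to change.** Put this first in 13.1.2: any patient with a DLT during the 10-week observation period is evaluable and counted, whatever the therapy received, the later reason for leaving, the supportive care given or the monitoring completed. Then state that the 85%, supportive-care and monitoring exclusions, and replacement, apply only to patients without a DLT.

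Alongside it, define what the 85% is measured in (doses, mg of the assigned dose, or the whole regimen), and reconcile 5.5.1 with 6.1 on whether a patient with a DLT is off treatment.

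The cost is a sentence or two of text. It adds no planned patients and changes no treatment.

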5.4.1 Extended Therapy

ABT-888 may be available for patients beyond the 10th course of maintenance if the patient is benefiting from the treatment, has at least clinical and radiographic stable disease at the end of course 10 and the investigator and subject agree to continue treatment for up to an additional 13 courses (total maximum duration of maintenance therapy is 23 courses). During this therapy, all study specific assessments will cease and procedures consistent with good clinical care will continue. Patients will be followed during this additional period for dates of drug administration, adverse events, laboratory results, date of disease progression, date of last follow up and date of death.

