5.5.2 Off-Treatment Data Submission Schedule

Patients will be followed for the resolution of all toxicities considered at least possibly related to ABT-888 occurring while on treatment and for 30 days after the last administration of study drug. Patients will be followed for 3 years from the initiation of protocol treatment for the monitoring of unexpected later developing toxicities or other morbidity and to document disease progression and survival. Data should be updated quarterly in the PBTC RDC database.

For patients who are eligible for extended therapy (5.4.1) they will be followed during this additional period for dates of drug administration, adverse events that are possibly, probably or definitely related to study drug, laboratory results, date of disease progression, and date of last follow up and date of death. At the completion of the additional 13 courses of therapy the patient is considered to have completed protocol therapy and should be taken off treatment (per protocol section 5.5). At the completion of the appropriate follow up period (per protocol section 5.6), the patient should be considered off study.

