9.2 Special Studies

9.2.1 Neuroimaging Studies

Standard MRI will be obtained within 2 weeks prior to registration, at the end of radiation therapy (week 10), within 1 week prior to courses 3, 5, and 8 of maintenance and at the end of treatment. MR perfusion and permeability studies and DTI will also be obtained at the same time points as standard MRI through week 26 (6 months from initiation of treatment).

For patients showing possible tumor progression on MRI during the first 6 months after the initiation of ABT-888 and irradiation (on scheduled MRI studies), the treating physician will have the option of allowing the patient to remain on study, continuing protocol therapy, and repeating disease reassessment in 4-6 weeks. The investigational sequences should be obtained on this additional scan which is completed due to possible pseudoprogression. 3T imaging is the preferred modality of choice.

Standard MR imaging will include Sagittal T1 MPRAGE, axial FLAIR, axial T2,

postgadolinium sagittal T1 MPRAGE (with reconstructions) and axial T2 images. Protocol standard parameters will be distributed to the sites and posted on the PBTC NIC website.

Volumetric analyses will be done at the Neuroimaging Center (NIC, Children's Hospital Boston) via the Vitrea (VitreaTM) workstation, from the axial FLAIR and T1-weighted post-contrast brain images.

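### Section 13.2 gives two censoring dates for PFS; the last-contact version can count time without disease assessment as progression-free (minor, secondary endpoint)

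*Combined protocol and SAP*

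**What the plan says.** Section 13.2 (Phase II Study Design/Endpoints) makes PFS a secondary endpoint and sets out its dates in one paragraph.

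- **Event date:** "the earliest date of failure (disease progression, death from any cause, or second malignancy").
- **Definition, patients without failure:** time runs "to the last assessment date for patients who have not failed".
- **Alternative therapy:** "Patients who start other anti-cancer therapy prior to disease progression will be censored in the Kaplan-Meier estimate of PFS", at the date that therapy began.
- **Kaplan-Meier sentence, patients without failure:** they "will be censored at their last date of contact in the Kaplan-Meier estimate of the PFS". The brackets in that sentence pair failure with PFS and death with OS, so last contact is applied to both endpoints.

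Three other places bear on how far the two dates can separate.

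- **Section 9.2.1:** after baseline and week 10, MRI is due "within 1 week prior to courses 3, 5, and 8 of maintenance and at the end of treatment". No later imaging schedule is fixed.
- **Section 5.4.1:** during extended therapy "all study specific assessments will cease and procedures consistent with good clinical care will continue". The study calendar (footnote 14) only recommends MRI at least every three months there.
- **Section 5.5.2:** "Patients will be followed for 3 years from the initiation of protocol treatment", and "Data should be updated quarterly in the PBTC RDC database". The stated purpose of that follow-up includes documenting progression as well as survival.

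**The concern.** The paragraph gives the same patients two different censoring dates, defines neither assessment nor contact, and does not say which rule prevails. Two analysts following the text could produce two PFS curves from one dataset, and the choice could be made after the data are seen.

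The rules also differ in merit. Last contact suits OS, because any contact establishes that the patient is alive. For PFS, a contact without a disease assessment does not establish that the patient is free of progression. Section 5.5.1 lets patients stop treatment unprogressed (toxicity, refusal, other illness, pregnancy, non-compliance, completion), and after that no imaging is scheduled. If progression goes undetected in that interval, the last-contact rule biases PFS upward. PFS also enters the exploratory biomarker analyses (Cox models in 13.4.2.1; log-rank and Cox in 13.4.3), so the ambiguity carries into those.

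**Working it through.** **The plan's own figures.** No sample size, power or boundary figure depends on PFS censoring, so there is none to reproduce. The one PFS figure is the background 1-year rate of 15.9 ± 3.1% in 140 patients (section 2.1). Its binomial SE is √(0.159 × 0.841 / 140) = 3.09%, as stated.

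**Who is affected.** A later death is a PFS event under either rule, and the final analysis waits for at least 2 years of follow-up or death (13.2.2). Barring loss to follow-up, the rules differ only for patients alive at about 24 months with no recorded progression. Patients alive at 24 months, out of 60:

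- at the historical OS of 10.21% (Table 20): 60 × 0.1021 ≈ 6;
- at an exponential median of 16.5 months: 60 × 0.5^(24/16.5) ≈ 22.

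Only those among them without recorded progression count. Patients who complete 10 four-week courses from week 11 finish at about week 50 with an end-of-treatment MRI. At 1 year the gap therefore comes mainly from patients who leave early; for completers it opens later.

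**Size at 1 year (assumed inputs).** Of n = 60 patients, k have no recorded failure, a last disease assessment at month t and contact beyond month 12. The other n − k follow exponential PFS, S(·).

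- Last assessment: {[(n − k)·S(t) + k]/n} × S(12)/S(t)
- Last contact: [(n − k)·S(12) + k]/n
- Difference: (k/n) × [1 − S(12)/S(t)], which is never negative

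Main case: k = 3, t = 4, S(12) = 0.16, so S(4) = 0.16^(1/3) = 0.543.

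- Last assessment: (57 × 0.543 + 3)/60 = 0.566; 0.566 × 0.16/0.543 = **16.7%**
- Last contact: (57 × 0.16 + 3)/60 = 12.12/60 = **20.2%**
- Difference: about 3.5 points. For scale, the binomial SE at n = 60 is √(0.16 × 0.84/60) = 4.7 points.

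Range, with t = 6 and S(12) = 0.159, so S(6) = 0.399:

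| k | Last assessment | Last contact | Difference (points) |
|---|---|---|---|
| 1 | 16.3% | 17.3% | 1.0 |
| 2 | 16.7% | 18.7% | 2.0 |
| 3 | 17.1% | 20.1% | 3.0 |
| 6 | 18.3% | 24.3% | 6.0 |

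**The case against.** Much of the case on the other side stands.

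- **A contact is not merely proof of life.** A reader might infer that it is, and that patients could go 3 years with no disease assessment. The documents do not support that. Section 5.5.2 includes progression in the purpose of follow-up, 5.4.1 collects the progression date during extended therapy, and 11.1.4 counts neurological worsening or rising steroid need as progression. What remains is narrower: no imaging schedule is fixed after treatment, and nothing requires each contact to include an assessment.
- **No comparison with 15.9% is planned.** A reader might also infer that 1-year PFS will be judged against that rate. It appears only as background. The historical comparison is for OS, by log-rank test (13.2.2); for PFS the plan promises a Kaplan-Meier estimate. The documents do not say how the 15.9% was censored, so any bias relative to it cannot be determined.
- **The illustration is demanding.** Three patients would be half of the roughly 6 two-year survivors expected at the historical rate, and none may have started other therapy, since they would then be censored at that date.
- **The definition already gives the better rule.** The later sentence may simply have merged two endpoints. That makes the repair easy, but the Kaplan-Meier sentence is the one that instructs the analyst, and as written it says last contact.

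**Conclusion.** The contradiction is in current text and holds. Of the two rules, last contact is the wrong one for PFS: for the same patients it can only leave the curve level or raise it, and it overstates PFS when progression goes undetected between the last assessment and the last contact. The difference at 1 year is about 3.5 points in the main illustration and 1 to 6 points over the range shown. These sizes rest on assumed patient counts, assessment times and exponential PFS; the documents give no such counts. In the biomarker analyses, PFS within a group can be lifted in the same way, but the direction of any between-group effect cannot be told from the documents.

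Severity is minor. A reader might infer that the trial's efficacy conclusion is at risk, but the OS analysis, the 60 patients, the Appendix G boundaries and the 87.72% power make no use of PFS.

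**What to change.** In the Kaplan-Meier sentence of section 13.2, separate the two endpoints. Censor PFS, for patients without a PFS event, at the last disease assessment (MRI or neurological examination) on or before the data cut-off, which agrees with the definition earlier in the paragraph. Keep last contact for OS only. The rule for patients who start other therapy stays as it is.

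The cost is one sentence and no new data. The downside is that slightly less PFS follow-up time is counted. The change should be made before the PFS data are analysed, so that the choice of rule cannot depend on the results.
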